Date: Approved Last on November 22, 2022

Title: Comparing Brief Relaxation period to Virtual Reality period in reducing dental anxiety prior to root canal treatment; a randomized control trial

NCT #: 05720897

Methods Protocol

Inclusion Criteria

In order to participate in the study, patients must have been between the ages of 18 to 90 years old and have the capacity to independently give consent for root canal treatment. The participant must have been proficient in English and have no visual or hearing impairments that would interfere with listening with earphones or utilizing virtual reality glasses. Subjects must also need non-surgical root canal treatment.

Exclusion Criteria

Subjects may not have participated in the study if they have a history of vertigo or severe motion sickness. They must not have required nitrous oxide sedation, nor pharmacologic anxiolytics or sedatives for treatment. In addition, self-reporting of any severe psychiatric disease, medical history of seizures, concussions, or severe neurological conditions, visual and hearing impairments, and reporting of a cardiac pacemaker or defibrillator, would rule out patients from this study.

Materials

The project will require the following: Oculus Quest2 (*Meta Quest; Meta2 VR Headset*); Maxwell 190319 Stereo Headphone, Black (*Amazon*), Dell Optiplex 7050 Computer, ComfortCuff 506N3 Series (*Criticare Systems Inc.*).

Sample Size

With a sample size of 28 patients per group completing the study, the study will have an 80% power to detect changes in the patient's self-reported anxiety as measured by their responses to the psychometrically validated STAI instrument of 3.6 (within each group an effect size of 0.55) and differences of a 5.0 between groups (an effect size of 0.77). The calculations are based on paired and two-sample t-test calculations, respectively, and these calculations assume a within-group standard deviation of 6.5 for change in STAI and a two-sided 5% significance level. To account for a 5% dropout rate, 30 patients will be enrolled per group.

Methodological Procedures for Relaxation Interventions: ABR vs RVR

Institutional Review Board (IRB) submission was secured after an internal Research Committee first gave approval of study.

Auditory Brief Relaxation (ABR)

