reviewed with the patient all related inclusion/exclusion criteria for this study in order to first determine if the participant might qualify for the study.

3. The researcher verbally reviewed and got written consent for both the Non-surgical Root Canal Therapy (NSRCT) – {standard of care procedure} and the research study.
4. If the subject qualified, the participant was selected randomly to be a part of the RVR or ABR group, as per the randomization sheet.
5. *T0*: Blood pressure and heart rate recordings were recorded by the student investigator & STAI and VAS completed by participant.
6. Intervention: VR headsets or earphones with AAR were applied by the investigator and the patient experienced the intervention (approximately 8 minutes).
7. *T1*: VAS completed by participant and BP & HR are recorded.
8. Administration of local anesthesia and non-surgical root canal therapy performed by endodontic resident and timer began for treatment.
9. *T2*: STAI, VAS, BP, HR all recorded at the end of the appointment which was after final radiograph.
10. Dismissal of patient and treatment stops. In order to test both study hypotheses, repeated measures of ANOVAs will be conducted to test for any changes in time across T1, T2, and T3 for STAI and VAS Scores, BP and HR within the ABR and RVR groups and to compare between the two groups. In addition, associations of the outcomes with socio-demographic and related factors data will be tested by adding these factors as covariates in additional repeated measures of ANOVAs. Specific socio-demographic and related factors data to be collected will include: Age, gender, race/ethnicity, previous experience with auditory relaxation and relaxation by virtual reality and length of time for endodontic treatment. Two-sided 5% significance levels will be used for all inferential statistical analyses.

Statistical Analysis

With a minimum sample size of 28 patients per group (ABR Group; n=30 & VRR Group; n=28) having completed the study, the study has an 80% power to detect changes in patient's self-reported anxiety as measured by their responses to the psychometrically validated STAI instrument of 3.6 within each group (with an effect size of 0.55) and differences of a 5.0

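### Neither analysis text names the between-arm contrast that the 80% power describes, the arm difference in STAI change from T0, and neither says how T0 enters that comparison

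*Combined protocol and SAP*

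**What the plan says.** Three parts of the document bear on how the arms are compared.

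- **Sample Size** (repeated at the start of Statistical Analysis): the between-group power is for a two-sample t-test, and the calculations "assume a within-group standard deviation of 6.5 for change in STAI". The quantity powered is therefore the arm difference in change.
- **Study Procedure and Protocol: Timeline, step 10**: repeated-measures ANOVAs are to test both hypotheses, looking at changes over time "for STAI and VAS Scores, BP and HR within the ABR and RVR groups and to compare between the two groups". No group-by-time term, change score or baseline adjustment is named. The times are labelled T1, T2 and T3, although T3 is defined nowhere and the rest of the document uses T0, T1 and T2.
- **Statistical Analysis**: because the outcomes were not normal, changes within each group were tested with Wilcoxon signed-rank tests, and the arms were compared with Mann-Whitney U tests separately at each time. Change also appears in an exploratory regression on demographic characteristics, but not in an arm comparison.

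T0 comes before the intervention. Step 5 has "Blood pressure and heart rate recordings were recorded by the student investigator & STAI and VAS completed by participant", and step 6 then delivers the audio or VR session. STAI is taken at T0 and T2 only; VAS, blood pressure and heart rate are taken at all three times.

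**The concern.** A two-group repeated-measures ANOVA offers two terms that could be called the comparison of the groups. The group-by-time interaction asks whether the arms changed differently. The group main effect asks whether the arms differ on average over all the times in the model. Step 10 does not choose between them. For STAI the distinction is sharp: with measurements only at T0 and T2, a repeated-measures model must include T0, and T0 can carry no intervention effect. A main effect would average a true T2 difference with a T0 difference of zero.

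The Mann-Whitney tests do not average in T0, but they do not adjust for it either. Their power depends on the spread of STAI at a single time, which the plan does not give, and not on the SD of change that it does give.

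At stake are whether the 80% describes the test used, and whether the baseline value collected on every patient helps the comparison that the trial exists to make.

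**Working it through.** **Inputs from the documents.** 28 completers per arm; STAI difference 5.0; SD of change 6.5; two-sided 5% (Sample Size). STAI at T0 and T2 only (timeline, steps 5, 7 and 9).

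**Assumptions.** Equal SDs at T0 and T2, no expected arm difference at T0, normal data, and a T0-T2 correlation r. The documents do not give r, so a range of 0.3 to 0.8 is shown.

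**1. The plan's own figures.**
- Between arms: d = 5.0/6.5 = 0.769; noncentrality 0.769 × √(28/2) = 2.88 on 54 df; power 80.7%. The smallest number per arm that reaches 80% is 28.
- Within arm: 3.6/6.5 = 0.554; paired t-test with n = 28; power 80.7%.
- Dropout: 28/0.95 = 29.5, rounded up to 30.

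All stated figures reproduce. With the 30 and 28 completers reported, between-arm power is 82.0%.

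**2. Group-by-time term, STAI.** With two times this is the t-test on T2 − T0, so d = 0.769 and power is 80.7% at every r.

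**3. Group main effect with T0 as a response level, STAI.**
- Expected difference: (0 + 5.0)/2 = 2.5.
- SD at one time: σ = 6.5/√(2(1−r)).
- SD of the T0/T2 average: σ√((1+r)/2).
- Hence d = 0.769 × √((1−r)/(1+r)).

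**4. T2 alone, unadjusted t-test.** d = 5.0/σ = 0.769 × √(2(1−r)).

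**5. T2 with T0 as a covariate.** The residual SD is σ√(1−r²), so d = 0.769 × √(2/(1+r)). The one degree of freedom spent on the covariate is ignored.

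Power at 28 per arm:

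| r | σ | Group-by-time | Group main effect (d) | T2 alone | T2 adjusted for T0 |
|---|---|---|---|---|---|
| 0.3 | 5.49 | 80.7% | 54.6% (0.564) | 91.7% | 93.9% |
| 0.5 | 6.50 | 80.7% | 37.2% (0.444) | 80.7% | 90.4% |
| 0.7 | 8.39 | 80.7% | 22.1% (0.323) | 59.1% | 86.6% |
| 0.8 | 10.28 | 80.7% | 15.6% (0.256) | 43.2% | 84.6% |

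The main effect would need about 51, 81, 152 and 240 per arm for 80% at these four correlations. It matches the stated power only at r = 0.

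**6. Simulation check (20,000 runs, normal data).** At r = 0.5 and 0.7, group-by-time gave 81.0% and 80.9%, the main effect 37.0% and 22.0%, and the Mann-Whitney U test at T2 78.3% and 56.2%.

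**The case against.** A reader might infer that step 10 commits the trial to a diluted test and that the 80% is therefore lost. The documents do not support that, for four reasons.

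- Step 10 selects neither term. Its subject is change over time, so comparing the groups can naturally mean comparing those changes. That is the interaction, and it delivers 80.7%. The power basis, being on change, favours this reading.
- Step 10 does not literally keep T0, since it lists T1 to T3. T0 enters only once the labels are corrected to T0, T1 and T2. For STAI that correction is forced, because the outcome has no other second level. For VAS, blood pressure and heart rate it is likely but remains an inference.
- The Statistical Analysis section says the arms were compared at each time by Mann-Whitney U tests. These do not average T0 with later values, so a difference present only at T1 would be tested at T1 in full.
- The 80% is attributed to t-tests. No power is claimed for an ANOVA main effect, or for VAS, blood pressure or heart rate.

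All four points stand, and they rule out dilution as an established fact. They do not close the gap. The two texts give different between-arm tests, and neither names the contrast that was powered. The Mann-Whitney test at T2 is not a comparison of change, and its power falls below 80% once r exceeds about 0.5.

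**Conclusion.** The point holds as an unspecified and unreconciled between-arm contrast. The 80% is correct for the arm difference in STAI change from T0, but no analysis text names that difference as the between-arm test, and neither says that a patient's T0 value is used when the arms are compared. Depending on how the text is read, power for the planned 5.0-point difference is 80.7% (group-by-time), about 55% to 16% (group main effect including T0), or about 92% to 43% (T2 alone by t-test). Adjusting T2 for T0 gives about 94% to 85%, which is above the change-score analysis throughout the range.

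These ranges rest on an assumed r of 0.3 to 0.8, equal SDs at the two times, no baseline difference and normality. The last is open to doubt here, since the plan itself reports non-normal outcomes. The 80.7% for change does not depend on r.

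**What to change.** State one between-arm analysis, in the same words, in step 10 and in the Statistical Analysis section:

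- **Preferred:** model the post-intervention values with T0 as a covariate. Use T2 for STAI, and T1 and T2 together for VAS, blood pressure and heart rate, with an unstructured covariance for the two times.
- **At minimum:** the arm difference in change from T0 (group-by-time), T0 to T2 for STAI, and T0 to T1 and T0 to T2 for the other outcomes. State that the group main effect is not the test.
- Report each as an arm difference with a 95% CI. If non-normality is the worry, use a rank-based or otherwise robust version of the same comparison.
- Say that the 80% refers to the difference in STAI change.
- Correct the labels T1, T2 and T3 to T0, T1 and T2.

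The cost is a few sentences of text and one model run per outcome. T0 is already collected for every outcome, so no extra patients, visits or measurements are needed. Because the Statistical Analysis section is written as completed work, any analysis added now should be marked as such.

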between groups (with an effect size of 0.77). The calculations are based on paired and two-sample t-test calculations, respectively, and these calculations assume a within-group standard deviation of 6.5 for change in STAI and a two-sided 5% significance level.

Chi-square tests and two-sample t-tests were used to compare the two groups by differences in demographic characteristics. Due to non-normality of the outcomes, Wilcoxon Signed Rank tests were used to test for changes in the outcomes over time within each group, and Mann-Whitney U tests were used to compare the outcomes between the two groups at each time. Additional exploratory analyses to evaluate the associations of demographic characteristics with changes in the outcomes were performed using cumulative logistic regression. A two-sided 5% significance level was used for all tests. Analyses were performed using SAS version 9.4 (SAS Institute, Inc., Cary, NC, USA).

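### The 80% power for STAI belongs to a comparison of changes, but the groups were compared on levels without adjustment for T0, and step 10 describes a different analysis

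*Combined protocol and SAP*

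**What the plan says.** **Power.** The Sample Size and Statistical Analysis sections give 80% power, with 28 completers per group, for a STAI change of 3.6 points within a group (paired t-test) and a difference of 5.0 points between groups (two-sample t-test). For both, "these calculations assume a within-group standard deviation of 6.5 for change in STAI". Completers are reported as "ABR Group; n=30 & VRR Group; n=28) having completed the study".

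**Tests reported.** In the Statistical Analysis section, "Wilcoxon Signed Rank tests were used to test for changes in the outcomes over time within each group". For setting one arm against the other, the same section says that "Mann-Whitney U tests were used to compare the outcomes between the two groups at each time". The reason given is "Due to non-normality of the outcomes". Changes appear elsewhere only in exploratory regressions on demographic characteristics. Every test is at two-sided 5%.

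**Step 10 of the Timeline.** A different analysis appears here. It opens "In order to test both study hypotheses" and continues "repeated measures of ANOVAs will be conducted to test for any changes in time across T1, T2, and T3 for STAI and VAS Scores". It covers comparisons within and between the groups.

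**Schedule.** STAI is completed at T0 (step 5) and at T2, after the final radiograph (step 9). At T1 (step 7) the entry is "VAS completed by participant and BP & HR are recorded", so there is no STAI reading then. There is no T3.

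**The concern.** An SD of change describes the T0-to-T2 difference in each patient. A Mann-Whitney test on T2 scores works on the spread of the scores themselves, which can be smaller or larger depending on how strongly T0 and T2 are correlated. The 80% therefore cannot be carried over to the test that was run. If the correlation is high, a non-significant group result may reflect low precision, while a reader believes the trial had 80% power.

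Non-normality is a good reason for using ranks. It does not explain leaving T0 unused, because changes or T0-adjusted values can also be ranked.

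The between-group comparison is the one that randomisation protects. Both arms receive an active intervention, and the second STAI follows the completed root canal. A fall from T0 to T2 within an arm therefore mixes the intervention with relief at finishing, the passage of time and regression to the mean.

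**Working it through.** **1. The plan's own figures.** Noncentral t, two-sided 5%, SD of change 6.5.
- Within group: 3.6/6.5 = 0.554; noncentrality 0.554 × √28 = 2.93; 27 df; power 80.7%.
- Between groups, 28/28: 5.0/6.5 = 0.769; noncentrality 0.769/√(2/28) = 2.88; 54 df; power 80.7%.
- Between groups, 30/28 completers: 0.769/√(1/30 + 1/28) = 2.93; 56 df; power 82.0%.

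The sample-size arithmetic is right for a t-test on change scores.

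**2. From change to level.** The T0-T2 correlation ρ is not in the documents, so I assume 0.3 to 0.8 and equal SDs at T0 and T2.
- SD of a T2 score = 6.5/√(2(1 − ρ)).
- Residual SD after adjusting for T0 = (SD of a T2 score) × √(1 − ρ²).

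Power for 5.0 points at 30/28, t-tests on normal data:

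| ρ | SD, T2 score | Residual SD | T2 levels | Change | ANCOVA |
|---|---|---|---|---|---|
| 0.3 | 5.49 | 5.24 | 93% | 82% | 95% |
| 0.5 | 6.50 | 5.63 | 82% | 82% | 91% |
| 0.7 | 8.39 | 5.99 | 61% | 82% | 88% |
| 0.8 | 10.28 | 6.17 | 44% | 82% | 86% |

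The levels t-test falls below 80% once ρ exceeds about 0.53.

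**3. The test actually used.** The outcomes are said to be non-normal, so the Mann-Whitney test on T2 levels was simulated for normal data and for an assumed gamma distribution (skewness 1.63). Rank-based ANCOVA adjusting for T0 was simulated alongside. Repeat runs differ by up to about 2 points.

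| ρ | Mann-Whitney, normal | Rank ANCOVA, normal | Mann-Whitney, skewed | Rank ANCOVA, skewed |
|---|---|---|---|---|
| 0.3 | 91% | 93% | 98% | 99% |
| 0.5 | 78% | 88% | 93% | 97% |
| 0.7 | 56% | 81% | 79% | 95% |
| 0.8 | 43% | 81% | 63% | 93% |

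Rank-based ANCOVA is ahead in every row, by 2, 10, 25 and 38 points with normal data and by 1, 4, 16 and 30 with skewed data. Ordinary ANCOVA is not always ahead: under skew at ρ = 0.5 it gives about 90% against 93% for Mann-Whitney.

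**4. Step 10 beside the Statistical Analysis section.** With two STAI readings, the group-by-time term of a repeated-measures ANOVA is the same test as the two-sample t-test on change. On that reading step 10 matches the power calculation (82% at 30/28), and the tests reported later do not. Step 10's labels T1, T2 and T3 do not match the schedule of T0, T1 and T2, and STAI is missing at T1. The Statistical Analysis section does not mention the ANOVA.

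**The case against.** **The power loss may not exist.** This stands in part. If ρ is 0.5 or less, a t-test on T2 levels meets the stated 80%; under the assumed skew, Mann-Whitney stays at about 79% or more up to ρ = 0.7. A reader might infer that the trial is underpowered or its group comparison biased. The documents support neither: comparing T2 levels between randomised groups is valid, and the direction of the power gap depends on a correlation they do not give. What remains is that the stated power is attached to the wrong test and T0 information is left unused.

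**The ANOVA was evidently replaced.** Step 10 is in the future tense and the Statistical Analysis section in the past tense, with a reason for rank tests. That inference is fair, and the time labels look like a numbering slip. But the text does not say that one analysis replaced the other, or when. One could also read step 10 as testing the group main effect, which would have much lower power. That is an unlikely reading, because step 10 is about changes over time, and nothing here rests on it.

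**T0 is not ignored.** Correct: testing at each time includes T0. The T0 score is compared between groups, but it does not enter the T2 comparison.

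**Within-group tests are routine.** They are, and a reader might infer that a within-arm fall will be presented as efficacy. The documents do not say so. The point is only what such a change can support.

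**Conclusion.** The mismatch is certain from the text: power is stated for a comparison of changes, while the reported group comparison is on levels at each time without T0 adjustment. The sample size itself is correctly calculated.

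The practical size is uncertain. Over the assumed correlations, power of the reported test for 5.0 points runs from about 91% down to 43% with normal data and from 98% down to 63% with the assumed skew. Rank-based adjustment for T0 stays at about 81% or more throughout. These figures rest on equal SDs at T0 and T2, 30 and 28 completers, and a correlation and skewed shape that the documents do not supply.

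The conflict with step 10 is a gap in documentation: the reader cannot tell whether and when the plan changed. On the within-group tests, the conclusion is limited: a T0-T2 change cannot by itself be attributed to either intervention.

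**What to change.** 1. Add a between-group comparison of T2 STAI adjusted for T0 STAI. Use rank-based ANCOVA as the test, and ANCOVA with a robust or bootstrap 95% confidence interval for the size of the difference in points. Show it beside the Mann-Whitney result, and disclose that it was chosen after the reported tests.
2. State that the 80% power applies to a t-test on change scores, not to the Mann-Whitney comparison of levels.
3. Say that the rank tests replaced the repeated-measures ANOVA of step 10, if that is so. Correct the time labels to T0, T1 and T2, and note that STAI has two readings.
4. Base the conclusion about ABR versus RVR on the between-group comparison, and report within-group changes as descriptive.

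Cost: one re-analysis of data already collected, plus wording. The added comparison must be labelled post hoc, so it carries less weight than a prespecified one. The lack of a STAI reading at T1 and of an untreated arm cannot be repaired now; both limit what can be concluded.

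### The 80% between-group power is for change in STAI, but the arms were compared by Mann-Whitney on scores at each time, unadjusted for T0, and the timeline section names a different analysis

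*Combined protocol and SAP*

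**What the plan says.** **Power.** The Sample Size section, repeated in Statistical Analysis, gives 80% power with 28 completers per group for "differences of a 5.0 between groups (an effect size of 0.77"). The method is a two-sample t-test at the two-sided 5% level, and "these calculations assume a within-group standard deviation of 6.5 for change in STAI".

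**Analysis in the Timeline section (last item).** "In order to test both study hypotheses, repeated measures of ANOVAs will be conducted to test for any changes in time". The same sentence applies these models "within the ABR and RVR groups and to compare between the two groups".

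**Analysis in the Statistical Analysis section.** Citing non-normality, it says that "Wilcoxon Signed Rank tests were used to test for changes in the outcomes over time within each group" and that "Mann-Whitney U tests were used to compare the outcomes between the two groups at each time". Cumulative logistic regression on changes appears only as an exploratory look at demographic associations.

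**Schedule.** T0 has STAI, VAS, blood pressure and heart rate. At T1, "VAS completed by participant and BP & HR are recorded", with no STAI. At T2, "STAI, VAS, BP, HR all recorded at the end of the appointment".

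**The concern.** The Statistical Analysis section keeps change for the within-group tests and compares arms on the score at each time. For STAI, the only outcome with a power statement, that leaves two between-arm tests. The T0 test comes before the intervention in randomised arms, so it can show only chance imbalance. The T2 test carries the treatment comparison and does not use the T0 score.

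The quantity that was powered (difference in change) is therefore not the quantity tested (difference in T2 score). The second statement of the 80% stands directly before the description of the rank tests, so it is easily read as their power. A null STAI result could then be read as coming from an 80%-powered comparison when the true figure is unknown.

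The Timeline section adds a second between-group method for the same hypotheses. Nothing makes the rank tests a pre-set fallback or says that they replace the ANOVAs.

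**Working it through.** **Inputs from the documents.** Two-sided alpha 0.05; 28 per arm (completers 30 and 28); between-group difference 5.0; within-group change 3.6; SD of change 6.5. **Not in the documents:** the SD of STAI at one time, and the T0–T2 correlation r. I take r from 0.3 to 0.8, with equal T0 and T2 variances.

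**1. The plan's own figures.** Effect sizes: 5.0/6.5 = 0.77 and 3.6/6.5 = 0.55. Noncentral-t power:
- two-sample, 28 per arm: 80.7% (30 and 28: 82.0%)
- paired, n = 28: 80.7% (80.1% with the rounded 0.55)

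The 80% is correct for t-tests on change.

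**2. Link to the ANOVA.** With STAI at only two times, the group-by-time F statistic is the square of the two-sample t on change. That term would match the 80%, but the Timeline section does not name it.

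**3. From SD of change to SD of a score.** Var(change) = 2·SD²·(1 − r), so SD = 6.5/√(2(1 − r)): 5.49 at r = 0.3, 6.50 at 0.5, 10.28 at 0.8.

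**4. Power for a T2 difference of 5.0, 28 per arm.** Normal data, 20,000 simulated trials per r; repeat runs agree to within about a percentage point.

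| r | Mann-Whitney on raw T2 | Rank-ANCOVA | ANCOVA |
|---|---|---|---|
| 0.3 | 90% | 92% | 94% |
| 0.4 | 85% | 90% | 92% |
| 0.5 | 78% | 88% | 90% |
| 0.6 | 68% | 85% | 88% |
| 0.7 | 56% | 82% | 86% |
| 0.8 | 41% | 78% | 84% |

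The raw test crosses 80% near r = 0.47 (80.6% at 0.47, 79.7% at 0.48; 40,000 runs). With 30 and 28 completers it gives 91%, 80% and 42% at r = 0.3, 0.5 and 0.8. Mann-Whitney on change from T0 gives about 78% at every r.

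**5. Non-normal data** (8,000 runs per r; raw Mann-Whitney / rank-ANCOVA at r = 0.3, 0.5, 0.8):
- skewed (gamma, shape 2): 96/97, 90/95, 56/92%
- uniform: 87/90, 73/84, 39/77%

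Under the null (10,000 runs, normal and skewed), the error rate was 4.9–5.4% for rank-ANCOVA and 4.7–5.2% for Mann-Whitney.

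**6. Precision.** ANCOVA on T0 narrows the confidence interval by about 1 − √(1 − r²): 5%, 13% and 40% at r = 0.3, 0.5 and 0.8.

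**7. Chance imbalance.** The SE of the T0 difference is √(2/28) = 0.267 SD. A 0.5 SD imbalance is z = 0.5/0.267 = 1.87, so one at least that large in either direction occurs in 6.1% of trials. Given exactly 0.5 SD and no treatment effect, the T2 z statistic has mean 1.87r and SD √(1 − r²). At r = 0.5 these are 0.935 and 0.866, so P(z > 1.96) is the normal tail beyond (1.96 − 0.935)/0.866 = 1.18, about 12%, and the other tail is negligible. The same steps give 8% at r = 0.3 and 22% at r = 0.8.

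**The case against.** The basis of the 80% is disclosed: both statements name the t-tests and the SD of change, and the figure reproduces. The Timeline text is prospective, whereas Statistical Analysis is in the past tense and gives a reason for rank tests, so the natural reading is that one replaced the other. The Mann-Whitney test is unbiased with 5% error overall, and its power is above 80% if r is below about 0.47. Mann-Whitney on change is the closest rank analogue of the powered test, and rank-ANCOVA has no real advantage over it at r = 0.8 (about 78% each). Adjusting every outcome still leaves at least seven between-arm tests (STAI once; VAS, blood pressure and heart rate twice each) with no hierarchy. Any new analysis is post hoc.

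Much of this stands. There is no arithmetic error, the direction of the power difference is unknown, and the switch has a stated reason. But non-normality explains leaving a normal-theory model; it does not explain leaving T0 out, since rank methods can use it. Replacement of the ANOVAs has to be inferred. Rank-ANCOVA had higher power than the raw T2 test in every case run, and than Mann-Whitney on change at the lower correlations. The lack of a hierarchy is a fair limit of the remedy.

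**Conclusion.** The concern holds and should be fixed. The stated 80% is right for a t-test on change in STAI and does not describe the between-arm test reported. Under normality, equal variances and 28 per arm, that test's power for a 5.0-point difference runs from about 90% (r = 0.3) to 41% (r = 0.8); the documents do not fix where in this range it lies. Rank-ANCOVA on the T0 score runs from 92% to 78%. Because r and the shape of the data are assumptions, these figures illustrate the uncertainty and do not show that power was lost. The trial's validity is not in question. What is lost is precision, protection against chance T0 imbalance, and a clear statement of which between-group analysis is the main one.

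**What to change.** - Reconcile the Timeline and Statistical Analysis sections into one between-group analysis, and say that it replaces the other. Compare each post-baseline score between arms, adjusted for its own T0 value: STAI at T2; VAS, blood pressure and heart rate at T1 and T2. State which result is the main one; the sample size calculation points to STAI.
- Given the reported non-normality, use rank-ANCOVA for the test (rank the T0 and follow-up scores over both arms, regress one set of ranks on the other, compare residuals between arms). Report the ANCOVA-adjusted difference with a bootstrap 95% confidence interval. A proportional-odds model with group and T0 score is an alternative.
- Drop the T0 significance test.
- Beside the analysis, state that the 80% applies to a t-test on change, or restate it for the adjusted analysis with the assumed r.
- Because the document describes analyses already done, label the adjusted result a post-hoc re-analysis and show it beside the Mann-Whitney result.

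**Cost.** A few lines of SAS on data already collected, and corrected wording in Sample Size, Timeline and Statistical Analysis. No new data and no more patients.
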